### INTRODUCTION

#### *Study Background*

In the past 3 decades, the disease pattern in 80% of developing countries is shifting from communicable to noncommunicable diseases, of which stroke is one of the most common debilitating diseases, the second most common cause of death, and the third most common cause of disability adjusted life years. Compared to other countries in Southeast Asia, Indonesia has the highest age- and sex-standardized mortality (193.3/100,000) and disability-adjusted life years lost (3,382.2/100,000), which are caused by stroke.

In the majority of stroke patients, the upper limb is more severely involved than the lower limb, as most strokes occur in the territory of the middle cerebral artery. Lawrence et al. found upper limb weakness in 77% of patients and lower limb weakness in 72%. About half of all stroke survivors also report challenges in upper extremity motor function six months post-stroke, which can include hemiparesis, spasticity, co-contraction, pain, or other limitations which impact quality of life.

Clinicians and patients struggle to determine if and when muscle activity and movement will return after a stroke. During the early weeks, movement can return rapidly and seemingly unexpectedly, which makes every twitch or sensation a potential positive sign.

Prediction which applied early, and preferably within the first week after stroke onset are most useful for rehabilitation and discharge planning. Early prediction is also important when considering the constantly decreasing length of hospital stay and improved acute care. The median time in stroke unit was reported to be 7 days in Sweden and 2–8 days in Australia in 2019. These numbers point out the need to implement simple and informative prognosis indicators during the first days after stroke onset.

In acute care, function-based clinical exams remain the standard for evaluating and monitoring muscle activity and movement. The Manual Muscle Test (MMT) and NIH Stroke Scale (NIHSS) are among the most common evaluation measures used in the United States. instructions. The Fugl-Meyer Assessment (FMA) also expands the repertoire of movements to evaluate synergistic or other inappropriate muscle activity. The FMA has shown promise for predicting recovery and future function of upper extremity in stroke patients.

Individuals with no volitional movement, however, the FMA-UE or MMT alone cannot determine whether muscle activity is present. MMT score of 0 can indicate severe paresis with no muscle activity, that the muscle activity is below the level necessary to produce observable contractions, or that the patient was unable to fully participate in the assessment. Patients with an MMT of 0, this can be frustrating as the patient and their clinical team take a “wait-and-see” approach to determine whether muscle activity will return.

Ongoing research continues to explore areas of brain plasticity, neural recovery mechanisms, and prognostication of stroke outcomes to maximize

recovery, while there has been simultaneous advancement in wearable sensor-based technologies that provide additional, non-invasive means of examining neuromuscular pathways and recovery processes following stroke.

One of these wearable sensor-based technologies is surface electromyography (sEMG). Surface electromyography (sEMG) provides a non-invasive window into the nervous system that can be used to monitor muscle activity, but is rarely used in acute care. Steele et al have demonstrated that deploying sEMG in acute care is both feasible and useful. They found that current technology can be used to comfortably and non-obtrusively monitor muscle activity, even for patients with no detectable muscle activity by traditional clinical assessments. They perceive opportunities in using sEMG to inform prognosis, enable biofeedback training, and provide metrics necessary for supporting and justifying care for further research.

### ***Problem Statement***

Nijland et al subsequently carried out a prospective study to determine if outcome in terms of upper limb function at 6 months after stroke can be predicted using clinical parameters measured within 72 hours after stroke in hospital stroke units. This study found that the probability of an ARAT score of at least 10 out of 57 at 6 months poststroke could be predicted by paretic finger extension (binarized at a score of 1 or more out of 2 on the UE-FMA) and paretic shoulder abduction (binarized at a score of at least 9 out of 33 on the Motricity Index) evaluated 2 days poststroke. The authors present a helpful table for making predictions for individual patients. The clinical usefulness of making this prediction, however, is unclear as

the range of functional abilities represented by an ARAT score between 10 and 57 is very wide, and neither model has been validated.

Stinear et al combined clinical predictors and corticospinal tract biomarkers to predict 1 of 4 upper limb functional outcome categories at 3 months poststroke. The Predict Recovery Potential (PREP) algorithm was developed in a study of 40 participants and externally validated in a subsequent study of 157 participants. The PREP2 algorithm begins with the Shoulder Abduction, Finger Extension score (SAFE) determined within 72 hours of stroke. Each of these movements made with the paretic upper limb is evaluated with manual muscle testing and scored out of 5 with the Medical Research Council grades. The scores are summed to determine the SAFE score, and if the score is at least 5 out of 10, the patient's age is all that is required to predict either an Excellent or Good upper limb outcome, but if the SAFE score is <5 out of 10, then transcranial magnetic stimulation is needed to test the function of the corticomotor system. A good outcome is predicted if motor-evoked potentials can be elicited in the paretic upper limb. The NIHSS score is used to predict either a limited or poor upper limb outcome if motor-evoked potentials cannot be elicited. The PREP2 algorithm is accurate for 75% of patients, and using it in clinical practice increases therapist confidence, allows tailoring of upper limb therapy, and is associated with a reduced length of stay. A recent follow-up study found that PREP2 predictions remained accurate for most patients at 2 years poststroke. A major limitation of PREP2 is that transcranial magnetic stimulation is not readily available in many clinical settings.

Adopting wearable sensors like sEMG in acute care will ultimately require that these sensors provide unique and valuable insights that are not available with current methods. Beyond detecting muscle activity, longitudinal evaluations will determine the diagnostic and prognostic value of sEMG in acute care.

Christina Papazian et al. study found that monitoring muscle activity with dual mode sensors of sEMG during acute care could detect contractions in the major arm muscles of stroke survivors, even among those who had no observable activity from clinical examination. In their exploratory analyses, they found modest correlations between contraction characteristics and future function for the participants with an MMT of 0.

Regarding the accessibility of sEMG devices, Hachi et al found that its met predefined criteria of being portable, affordable, and easy to operate. This suggests that accessibility or price does not constitute in itself a barrier for the use of sEMG in the clinical practice. Recently, clinicians have recognized the potential of sEMG as a prognostic tool, but there is limited study has explained correlation of sEMG parameters as a predictor of upper extremity motor recovery in adult acute stroke patients.

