### ***Study Benefits***

This study has numerous benefits, it can help us gain a better understanding of complex issues, develop new technique, determine discharge planning, improve outcome of rehabilitation program, and inform public policy.

The results of this study are expected to enrich our knowledge and become a base for future research. The results of this study are also expected to be an aid in determine prognostication to promote functional outcomes in stroke patients.

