**Hypothesis :**

Based on the framework and premises above, the hypothesis is formulated as follows:

H0 : sEMG parameters cannot predicts upper extremity motor function recovery in stroke patients

H1: sEMG parameters can predicts upper extremity motor function recovery in stroke patients (premise 1,2,3,4,5)

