## **Data Analysis**

Before data analysis is carried out, the data is checked for completeness and accuracy, tabulated, coded, and entered into the computer. The next data analysis aims to describe the dependent and independent variables so that it can help further analysis in more depth. Apart from that, descriptive analysis is also used to determine the characteristics of the research subjects, who are the research samples.

Data analysis to see an overview of the proportions of each variable that will be presented descriptively can be broken down into descriptive analysis and hypothesis testing. Numerical scale data such as age and others are presented with a mean and standard deviation, a maximum value, and a minimum value. The sample characteristic data in the form of categorical data is presented in a frequency distribution table. Data is recorded in the research form that has been created, then editing, verification, coding, and data entry are carried out, and then data analysis

is carried out. Statistical analysis according to research objectives and research hypotheses Data are presented as percentages (%) for categorical variables and mean  $\pm$  standard deviation (SD) for continuous variables. Statistical analysis begins with this normality test aims to find out whether the data is normally distributed or not. The statistical test used to test the data is normally distributed or not, with Shapiro Wilks (because n is less than 50). Numerical variables between pairs of two groups is compared using the paired T test if the data is normally distributed and the alternative Wilcoxon test. Numerical variables between pairs of more than two groups is compared using the repeated ANOVA test if the data is normally distributed and the alternative Fredman test. The McNemar and Marginal Homogeneity tests are used for paired categorical data. The significance of statistical test results is determined based on a p value of  $<0.05$ .

The data obtained was recorded in a special form and then processed using the SPSS version 24.0 for Windows program.

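### The plan's only threshold, p<0.05 on tests of change over time in about 30 patients, cannot show that sEMG predicts recovery, and no prediction error or validation is planned

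*Combined protocol and SAP*

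**What the plan says.** The Research Question, Study Objective and Hypothesis sections all ask about prediction; the alternative hypothesis reads "H1: sEMG parameters can predicts upper extremity motor function recovery in stroke patients". Study Benefits adds: "The results of this study are also expected to be an aid in determine prognostication to promote functional outcomes in stroke patients".

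The Problem Statement says the clinical usefulness of an early ARAT-based model is unclear because "the range of functional abilities represented by an ARAT score between 10 and 57 is very wide, and neither model has been validated". It then describes a later algorithm as externally validated and reports its performance in patients: "The PREP2 algorithm is accurate for 75% of patients".

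For its own data, the Data Analysis section gives descriptive summaries, a normality test and three families of paired test. Two time points are "compared using the paired T test if the data is normally distributed and the alternative Wilcoxon test". For more occasions, "Numerical variables between pairs of more than two groups is compared using the repeated ANOVA test", with Friedman as the alternative. McNemar and marginal homogeneity tests cover paired categories. The one threshold is this: "The significance of statistical test results is determined based on a p value of" less than 0.05. The note to the dummy results table (Table 2) repeats it for the time-point columns. Neither place contains a correlation, regression, accuracy measure, prediction error, cut-off, resampling step or held-out sample.

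**The concern.** A claim to predict recovery needs a link between an early measurement and a later outcome in the same patient, and some measure of how close the forecast comes. The planned tests ask whether the average of each variable moves between visits. Most patients improve after a stroke, and the Literature Review expects the largest gains in the first weeks, so such movement is likely whether or not early sEMG says anything about later function.

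If p<0.05 is taken as the answer to H1, the study could report that sEMG predicts recovery when it does not narrow the forecast for a patient at all. If a correlation is added and judged by p<0.05, it could do so when the forecast is barely narrowed. Either result would have the two weaknesses that the Problem Statement names, a wide range of possible outcomes and no validation, while being offered as an aid to prognosis.

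**Working it through.** **Inputs.** From Sample Size Determination: two-sided alpha 0.05 (Z = 1.96), power 95% (Z = 1.64), difference 1, SD 1, 10% allowance, final minimum 30. From Outcome Measures and Table 4: three sEMG parameters on five muscles (15 values per visit), five visits to 3 months. From Table 4: FMA-UE bands of 25 or less, 26–45 and 46–66, on a 66-point scale. The documents give no SD for 3-month FMA-UE, so 10, 15 and 20 points are assumed.

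**The plan's own figure.** n = ((1.96 + 1.64) × 1 / 1)² = 12.96, so 13; 13 + 1.3 = 14.3, so 15. Both reproduce. They size a mean paired change of 1 SD, not prediction. The final 30 is a quoted rule of thumb with no formula.

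**Planned paired t test at n=30.** Significance needs a mean change of t/√n = 2.045/√30 = 0.37 SD of the changes. The outcome of the same patients does not enter the test. For a parameter independent of recovery, the probability of p<0.05 (noncentral t, confirmed by 20,000 simulated studies) is:

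| Mean change (SD) | Probability of p<0.05 |
|---|---|
| 0 | 0.05 |
| 0.3 | 0.36 |
| 0.5 | 0.75 |
| 0.8 | 0.99 |
| 1.0 (planning effect) | over 0.99 |

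The first row also works the other way. A day-3 parameter that forecasts recovery well but does not change on average would be significant only 5% of the time.

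**If an association test were added and judged by p<0.05.** The smallest significant correlation at n=30 is r = t/√(t² + 28) with t = 2.048, which gives 0.361 and R² = 0.130. At n=27 (10% lost) it is 0.381 and R² = 0.145.

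The half-width of the 95% prediction interval for one patient, at the predictor mean, in outcome SDs is:

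- with the parameter: 2.048 × √((1 − 0.130) × 29/28) × √(1 + 1/30) = 1.98
- with no predictor: 2.045 × √(1 + 1/30) = 2.08

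The ratio is 0.95, so the interval is about 5% narrower.

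| Assumed FMA-UE SD | With parameter | Without |
|---|---|---|
| 10 | ±19.8 | ±20.8 |
| 15 | ±29.6 | ±31.2 |
| 20 | ±39.5 | ±41.6 |

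At SD 15 the interval touches all three FMA-UE bands when the predicted score lies between about 17 and 54; at SD 20, between about 7 and 64.

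**Number of predictors.** With k pure-noise predictors, expected apparent R² is k/(n − 1): 3/29 = 0.10, or 15/29 = 0.52 for all 15 sEMG values. Median leave-one-out R² in simulation is about −0.2 and −1.4. This bears on how a model should be reported, not on the p<0.05 threshold.

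**The case against.** **The criterion is inferred.** A reader might infer that the protocol defines successful prediction as p<0.05. It does not. No sentence says when H1 is accepted; p<0.05 is simply the only threshold given. This stands, and the point is worded accordingly.

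**The root defect is that no prediction analysis is planned.** That is also correct. The correlation and prediction-interval figures describe an analysis the plan does not contain. They are kept only to show that adding a correlation judged at p<0.05 would not be enough.

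**The charge of a double standard can be pushed too far.** A reader might infer that the protocol faults all earlier tools. Its remark about range and validation covers only the models in that paragraph. The later algorithm is described as externally validated, and its stated limitation is the need for transcranial magnetic stimulation. The 75% accuracy is reported as background, not set as a target. That algorithm was developed in 40 participants and then validated in 157, so the lack of external validation at this stage is not itself inconsistent.

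**Overfitting is not evidence against the threshold.** A reader might infer from the apparent R² of 0.52 that p<0.05 is easily reached with 15 noise predictors. The overall F test still rejects at 5%.

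**The ambition is partly limited.** Study Benefits also presents the results as a basis for later research, and 30 is a minimum under consecutive sampling. Both are fair, but neither supplies a measure of prediction.

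**Conclusion.** The concern holds in this form: the plan asks whether sEMG can predict recovery, and its only threshold belongs to tests that do not address that question. Followed exactly, it could be read as supporting prediction from a parameter with no relation to outcome, with probability about 0.75 at a mean change of 0.5 SD and over 0.99 at 1 SD. Those figures assume n=30, normally distributed changes and the paired t test.

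A substituted association test would still admit a parameter that explains 13% of the variance and leaves a patient's forecast at ±20, 30 or 40 FMA-UE points. That rests on a linear model with normal errors and on the assumed SDs of 10, 15 and 20. The claim that the interval spans all three severity bands depends on the SD and on the predicted score.

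The change should be made before analysis. It decides whether the stated objective can be answered from data the study already collects.

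**What to change.** In Data Analysis:

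- State that H1 is assessed by a model of 3-month FMA-UE on one to three day-3 sEMG parameters, named before the data are seen and added to day-3 FMA-UE (or MMT). The comparison with the clinical score matters because the Problem Statement requires sensors to offer insight that current methods lack, and sEMG could otherwise do well merely by mirroring initial severity.
- Report bootstrap-corrected or leave-one-out R² and mean absolute error with 95% confidence intervals, with and without the sEMG terms, and the 95% prediction interval in FMA-UE points.
- State that p<0.05 alone, and p<0.05 for change over time in particular, does not support a claim of prediction. The planned paired tests can stay as descriptions of recovery.
- Label the result exploratory model development that needs external validation, and word Study Benefits to match.

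The documents give no figure from which to set a required level of accuracy, so the result becomes an estimate with its uncertainty and not a yes/no finding on H1.

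Cost: some wording, a row in the results table and a short resampling script. All the measurements are already scheduled. Reported performance will be less favourable than in-sample figures, and imprecise. In a simulation at n=30 with one predictor and a true correlation of 0.5, leave-one-out R² ran from about −0.12 to 0.48 (95% range).

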### ***Research Question***

More specifically, the following research question needs to be addressed :

Can sEMG parameters predict upper extremity motor function recovery in acute stroke patients?

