## LITERATURE REVIEW

### Upper Extremity Motor Impairment Post Stroke

Upper extremity weakness is the most common impairment of stroke patients, which plays an important role in motor function deficiency and has a detrimental effect on the quality of life.

Upper extremity impairments after stroke are the cause of activity limitations, participation restrictions, and reduced independence in daily life with regard to use of the affected upper extremity after stroke, so a clear understanding of the underlying impairments is necessary to provide appropriate treatment. Understanding upper extremity impairments in any given patient is complex for two reasons:

- 1) The impairments are not static, for example as motor recovery proceeds, the type and nature of the impairments may change, therefore the treatment needs to evolve to target the impairment contributing to dysfunction at a given point in time.
- 2) Multiple impairments may be present simultaneously, for example a patient may present with weakness of the arm and hand immediately after a stroke, which may not have resolved when spasticity sets in a few weeks or months later, hence there may be a layering of impairments over time making it difficult to decide what to treat first.

It is useful to review the progression of motor recovery as described by Twitchell and Brunnstrom to understand how impairments may be layered over time (Figure 1).

[figure not shown]

Figure 1. Sequential progression of motor recovery. Quoted from: Raghavan P. Upper Limb Motor Impairment After Stroke. *Phys Med Rehabil Clin N Am.* 2015;26(4):599-610

Prabhakaran et al. proposed a proportional recovery rule. According to this rule, the majority of stroke survivors are expected to recover approximately 70% of their maximum potentials at 3 months after a stroke.

A rule of thumb in stroke recovery is that patients with mild deficits are more likely to make a good recovery than patients with initially more severe deficits (Figure 2). The most significant improvements occur in the first few weeks post-stroke, often reaching a relative plateau after 3 months with less significant recovery subsequently. After 6 months, spontaneous recovery is usually at its limit, leading to a more or less stable, for example, chronic deficit.

[figure not shown]

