## Study Variable

Independent variables:

1. Type of stroke
2. Stroke severity
3. Recurrent stroke

Dependent variables:

1. MMT score
2. FMA-UE score
3. Electrical activity of deltoid muscle
4. Electrical activity of biceps muscle
5. Electrical activity of triceps muscle
6. Electrical activity of wrist flexors muscle
7. Electrical activity of wrist extensors muscle

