    - 00:07:00 (elbow flexion)
    - 00:08:00 (rest)
    - 00:09:00 (elbow flexion)
    - 00:10:00 (rest)
    - 00:11:00 (elbow flexion)
    - 00:12:00 (rest)
    - 00:13:00 (elbow extension)
    - 00:14:00 (rest)
    - 00:15:00 (elbow extension)
    - 00:16:00 (rest)
    - 00:17:00 (elbow extension)
    - 00:18:00 (rest)
    - 00:19:00 (wrist flexion)

- 00:20:00 (rest)
- 00:21:00 (wrist flexion)
- 00:22:00 (rest)
- 00:23:00 (wrist flexion)
- 00:24:00 (rest)
- 00:25:00 (wrist extension)
- 00:26:00 (rest)
- 00:27:00 (wrist extension)
- 00:28:00 rest
- 00:29:00 (wrist extension)
- 00:30:00 (rest)

[figure not shown]

Figure 6. The five movements tested in the experimental setting. Shoulder flexion (a), elbow flexion (b), elbow extension (c), wrist flexion (d), wrist extension (e).

j. The electrodes are released and the scratch area is checked to see if there are any signs of irritation

- k. The subjects are informed that the data collection has been completed, the sEMG engine cleaned up.
8. Surface EMG's signal recording results in digital form were submitted to the ITB Engineering team for the processing of the signal. The results of the electrical activity features of the muscle are contraction, length of contraction and amplitude will be analyzed.
9. All assessment (MMT, FMA UE and sEMG) is carried out at 3 days of stroke onset, the day of discharge from hospital, 1 month, 2 months and 3 months after stroke onset.

[figure not shown]

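### No planned model relates day-3 sEMG to 3-month FMA-UE, and day-3 FMA-UE and MMT have no role as reference predictors

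*Combined protocol and SAP*

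**What the plan says.** The Research Question is "Can sEMG parameters predict upper extremity motor function recovery in acute stroke patients", and the Hypothesis section answers in the same terms: "H1: sEMG parameters can predicts upper extremity motor function recovery in stroke patients". Neither names a reference predictor.

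The protocol describes bedside information as already prognostic. Study Background: "The FMA has shown promise for predicting recovery and future function of upper extremity in stroke patients". The literature review on upper extremity impairment: "patients with mild deficits are more likely to make a good recovery than patients with initially more severe deficits". The Problem Statement reviews tools built on finger extension, shoulder abduction, manual muscle testing and the NIHSS. It then says that adopting sEMG in acute care will in the end require that "these sensors provide unique and valuable insights that are not available with current methods".

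The benchmark data are collected. Research Work Procedure, item 9: "All assessment (MMT, FMA UE and sEMG) is carried out at 3 days of stroke onset, the day of discharge from hospital", and again at 1, 2 and 3 months. However, Study Variable places MMT, FMA-UE and the electrical activity of all five muscle groups together under "Dependent variables". The independent variables are stroke type, stroke severity and recurrent stroke.

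Data Analysis and the note to Table 2 give descriptive statistics, Shapiro-Wilk, paired t or Wilcoxon, repeated-measures ANOVA or Friedman, and McNemar or marginal homogeneity. In Table 2 each measure is compared with itself across visits. There is no correlation, regression or adjusted model. The confounder list in Study participants does not include initial motor severity.

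**The concern.** The literature review on surface EMG says that fewer recruited motor units give lower amplitude, so amplitude should be higher in less weak arms. The protocol also says that milder deficits recover better. An sEMG parameter could therefore be associated with 3-month FMA-UE only because both reflect how severe the stroke was at day 3. A bedside score shows that without electrodes.

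The planned tests cannot separate these explanations, because none relates sEMG to FMA-UE. The obvious repair, a simple correlation of day-3 sEMG with 3-month FMA-UE, would not separate them either. At stake is whether a positive result says anything about what sEMG adds, which is the question that the Problem Statement ties to adoption.

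**Working it through.** **1. The plan's own figure.** Sample Size Determination uses ((Zα + Zβ)·S/(X1 − X2))² with 1.96, 1.64, S = 1 and difference 1: 3.60² = 12.96, so 13. Adding 10% gives 14.3, so 15. This reproduces. It sizes a within-patient mean change of one SD, not prediction. The final 30 comes from a rule of thumb.

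**2. Unadjusted association, 3-month level.** The documents give no correlations, so these are assumptions: a = correlation of sEMG with day-3 FMA-UE, 0.5-0.7; b = correlation of day-3 with 3-month FMA-UE, 0.6-0.8. sEMG is given no added value, that is, independence from the 3-month score given the day-3 score. The induced correlation is then r = a·b. Approximate power at n = 30, two-sided 0.05, is Φ(atanh(r)·√27 − 1.96). The simulation used 20,000 studies per setting with trivariate normal data.

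| a, b | r = a·b | Approximation | Simulated, unadjusted | Simulated, given day-3 FMA-UE |
|---|---|---|---|---|
| 0.5, 0.6 | 0.30 | 36% | 37% | about 5% |
| 0.6, 0.8 | 0.48 | 78% | 79% | about 5% |
| 0.7, 0.8 | 0.56 | 91% | 92% | about 5% |

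The first and last rows are the extremes of the assumed ranges. Wider assumptions (0.4 with 0.6, up to 0.8 with 0.9) give 25% to 99.7%.

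**3. Same settings, change from day 3.** With equal variances at both times, the correlation of sEMG with change is a(b − 1)/√(2 − 2b) = −a·√((1 − b)/2).

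- 0.5, 0.6: −0.5·√0.20 = −0.22
- 0.6, 0.8: −0.6·√0.10 = −0.19
- 0.7, 0.8: −0.7·√0.10 = −0.22

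The simulated significance rates are about 22%, 17% and 22%. A positive sEMG association appears in under 0.3% of studies. These rates belong to the three settings and are not bounds: other pairs in the ranges run from −0.5·√0.10 = −0.16 to −0.7·√0.20 = −0.31. The sign is negative throughout.

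**4. Why adjustment serves both outcomes.** If the 3-month score is β·(day 3) + γ·sEMG + error, then change is (β − 1)·(day 3) + γ·sEMG + error. The sEMG coefficient γ is the same.

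**5. What 30 patients can show after adjustment.** For a partial correlation with one covariate, power is about Φ(atanh(r)·√(30 − 3 − 1) − 1.96).

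- r = 0.3: 0.310 × 5.099 − 1.96 = −0.38, so 35%.
- r = 0.5: 0.549 × 5.099 − 1.96 = 0.84, so 80%.
- For 80% power at r = 0.3: ((1.96 + 0.84)/0.310)² + 4, which is 86 patients.
- With 27 completers (10% loss): 32% at r = 0.3 and 75% at r = 0.5.

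**The case against.** The strongest reply is that the plan contains no sEMG-outcome test, so nothing in it could report a severity proxy as a predictor. That stands. A reader might infer that the plan as written would produce such a result, but the documents do not support this. The problem arises only if an unadjusted association is added or used to support H1.

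Second, the adoption remark is cited background about eventual use, and the stated question is only whether sEMG can predict. Testing association first and added value later is legitimate. This also stands: it is a reason to add to H1, not to replace it.

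Third, four inferences go further than the text.
- A day-3 NIHSS is not documented. The examination form in Lampiran 1 has an NIHSS field, but the visit schedule names only MMT, FMA-UE and sEMG.
- Severity is not absent from the design. Study Variable lists it as independent and Operational Definition defines it by NIHSS. But Data Analysis does not use it, and Table 3 lists it beside a p-value column with no stated comparison.
- Study Background does not say that bedside scales are uninformative at MMT 0. It says only that FMA-UE or MMT alone cannot establish whether muscle activity is present.
- Not every severity-related parameter would be declared a predictor: at the low end of the assumed range, 37% would be.

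Fourth, the level result does not carry over to change. Operational Definition describes recovery as improvement but grades it by score level, so both readings are open.

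Fifth, the return to 5% is built into the simulation. If FMA-UE measured severity with an assumed reliability of 0.8, the adjusted test would still reject in 7-19% of studies, and with 0.9 in 6-9%.

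**Conclusion.** The point holds in a conditional form. The plan has neither a model of 3-month FMA-UE on day-3 sEMG nor a day-3 benchmark, so no planned result can distinguish sEMG prognosis from initial severity. If an unadjusted association is used to support H1, a parameter with no added value would be significant in about 37-92% of studies for the 3-month level. For change it would be about 17-22% in the three settings, mostly with the opposite sign.

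These sizes rest on assumed correlations, normal data, n = 30 with no loss, and, for change, equal variances. That the benchmark is absent rests on the text alone. This is a worthwhile and inexpensive improvement; it does not show that a planned analysis gives a false answer.

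**What to change.** Keep H1 and make these additions.

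- **Data Analysis:** pre-specify a nested model of 3-month FMA-UE on day-3 FMA-UE, with and without one day-3 sEMG parameter. Choose that parameter in advance from the 15 available (five muscle groups by three measures). Report the partial association, or the change in R-squared, with its confidence interval, beside the unadjusted association.
- **Study Variable:** list day-3 FMA-UE as the reference predictor and day-3 MMT as a sensitivity check. Use NIHSS only if its time of assessment is fixed.
- **Patients with MMT 0:** repeat the comparison descriptively.
- **Labelling:** call the model exploratory, and state that a null result is not evidence of no added value.

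No new visits, patients or measurements are needed. The costs are a new model in Data Analysis, the discipline of choosing one parameter, one degree of freedom, an sEMG effect that will look smaller, and limited precision at 30 patients. Some residual confounding remains if day-3 FMA-UE measures severity imperfectly.
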